8.6.3 Missed Study Drug Doses

Missed doses of study drug should be recorded. Our intention is to tightly adhere to the weekly schedule of medication administration.

8.7 Management of known adverse events associated with mTOR inhibitors

8.7.1 Management of Hepatitis reactivation/flare

Monitoring and prophylactic treatment for hepatitis B reactivation should occur based on the institutional standard for pediatric participants and in consultation with a pediatric gastrointestinal specialist and/or pediatric infectious disease.

8.7.2 Management of stomatitis/oral mucositis/mouth ulcers

Stomatitis/oral mucositis/mouth ulcers due to mTOR inhibitors should be treated using local supportive care. Please note that investigators in earlier trials have described the oral toxicities associated with mTOR inhibitors as mouth ulcers, rather than mucositis or stomatitis. If your examination reveals mouth ulcers rather than a more general inflammation of the mouth, please classify the adverse event as such. Please follow the paradigm below for treatment of stomatitis/oral mucositis/mouth ulcers:

1. For mild toxicity (Grade 1), conservative measures such as non-alcoholic mouth wash or salt water (0.9%) mouthwash several times a day until resolution is recommended
2. For more severe toxicity (Grade 2 in which case participants have pain but are able to maintain adequate oral alimentation, or Grade 3 in which case participants cannot maintain adequate oral alimentation), the suggested treatments are topical analgesic mouth treatments (i.e., local anesthetics such as benzocaine, butyl aminobenzoate, tetracaine hydrochloride, menthol, or

phenol) with or without topical corticosteroids, such as triamcinolone oral paste 0.1% (Kenalog in Orabase®).

3. Agents containing hydrogen peroxide, iodine, and thyme derivatives may tend to worsen mouth ulcers. It is preferable to avoid these agents.

4. Antifungal agents must be avoided unless a fungal infection is diagnosed. In particular, systemic imidazole antifungal agents (ketoconazole, fluconazole, itraconazole, etc.) should be avoided in all participants due to their strong inhibition of mTOR inhibitor metabolism, thereby leading to higher mTOR inhibitor exposures. Therefore, topical antifungal agents are preferred if an infection is diagnosed. Similarly, antiviral agents such as acyclovir should be avoided unless a viral infection is diagnosed.

Note: Stomatitis/oral mucositis should be appropriately graded using the functional grading given on the NCI-CTCAE for adverse events, v5.

8.7.3 Management of hyperlipidemia and hyperglycemia

Treatment of hyperlipidemia should take into account the pre-treatment status and dietary habits. Blood tests to monitor hyperlipidemia must be taken in the fasting state. Hyperlipidemia and hypertriglyceridemia should be treated according to local best clinical practice. Participants should be monitored clinically and through serum chemistry for the development of rhabdomyolysis and other adverse events as required in the product label/data sheets for HMGCoA reductase inhibitors. Hyperglycemia has been reported in clinical trials. Monitoring of fasting serum glucose is recommended prior to the start of mTOR inhibitor dosing and periodically thereafter. Optimal glycemic control should be achieved before starting study drug dosing.

8.7.4 Management of non-infectious pneumonitis

Non-infectious pneumonitis is a class effect of rapamycin derivatives. Cases of non-infectious pneumonitis (including interstitial lung disease) have also been described in participants taking mTOR inhibitors. Some of these have been severe and on rare occasions, a fatal outcome was observed.

A diagnosis of non-infectious pneumonitis should be considered in participants presenting with nonspecific respiratory signs and symptoms such as hypoxia, pleural effusion, cough or dyspnea, and in whom infectious, neoplastic and other non-medicinal causes have been excluded by means of appropriate investigations. Participants should be advised to report promptly any new or worsening respiratory symptoms. Participants who develop radiological changes suggestive of non-infectious pneumonitis and have few or no symptoms may continue mTOR inhibitor dosing without dose alteration. If symptoms are moderate (Grade 2), consideration should be given to interruption of dosing until symptoms improve. The use of corticosteroids may be indicated. mTOR inhibitor may be reintroduced once at a reduced dose until recovery to Grade 1 or better. For cases where symptoms of non-infectious pneumonitis are severe (Grade 3), mTOR inhibitor dosing should be discontinued and the use of corticosteroids may be indicated until clinical symptoms resolve. Dosing with mTOR inhibitors may be re-initiated at a reduced dose depending on individual clinical circumstances.

Table 5. Pneumonitis Management and ABI-009 Dosing

Pneumonitis Grade	Required Investigations	Management of Pneumonitis	ABI-009 Dose Adjustment
Grade 1	CT scans with lung windows and pulmonary function testing including spirometry, DLCO, and room air O ₂ saturation at rest. Repeat chest x-ray/CT scan every 2 cycles until return to baseline.	No specific therapy required.	Administer 100% of ABI-009 dose
Grade 2	CT scans with lung windows and pulmonary function testing including spirometry, DLCO, and room air O ₂ saturation at rest. Repeat chest x-ray/CT scan every cycle until return to baseline. Consider bronchoscopy.	Symptomatic therapy. If cough is troublesome prescribe corticosteroids.	Reduce ABI-009 dose until recovery to \leq Grade 1. ABI-009 may also be interrupted if symptoms are troublesome. Participants will be withdrawn from the study if they fail to recover to \leq Grade 1 within 3 weeks.
Grade 3	CT scans with lung windows and pulmonary function testing including spirometry, DLCO, and room air O ₂ saturation at rest. Repeat chest x-ray/CT scan every cycle until return to baseline. Bronchoscopy recommended.	Prescribe corticosteroids if infection is ruled out. Taper as medically indicated.	Hold ABI-009 until recovery to \leq Grade 1. ABI-009 may also be restarted within 3 weeks at a reduced dose (by one level) if evidence of clinical benefit. Participants will be withdrawn from the study if they fail to recover to \leq Grade 1 within 3 weeks.
Grade 4	CT scans with lung windows and pulmonary function testing including spirometry, DLCO, and room air O ₂ saturation at rest. Repeat chest x-ray/CT scan every cycle until return to baseline. Bronchoscopy recommended.	Prescribe corticosteroids if infection is ruled out. Taper as medically indicated.	Discontinue ABI-009

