8.6 Dose Modification or Discontinuation of Study Drug

For participants who are unable to tolerate the protocol-specified dosing schedule secondary to DLT, dose adjustments are permitted in order to keep the participant on study drug. If administration of ABI-009 must be interrupted due to DLT, drug dosing will be interrupted or modified according to rules described in the table below. Toxicity will be assessed using the NIH/NCI Common Terminology Criteria for Adverse Events, version 5.0. If a participant requires a dose delay of ≥ 3 weeks from the intended day of the next scheduled dose, then the participant must be discontinued from the study or may resume only with the approval of the Principle Investigator.

Table 4: Hematological and non-hematological toxicities and ABI-009 dosing adjustments

TOXICITY	ACTIONS
Non-hematological toxicity	
Grade 2	If the toxicity is tolerable to the participant, maintain the same dose. If

(pneumonitis management detailed separately in 8.7.4)	the toxicity is intolerable to participant, interrupt ABI-009 until recovery to grade 1 or better. Then reintroduce ABI-009 at same dose. If event returns to intolerable grade 2, then interrupt ABI-009 until recovery to grade 1 or better. Then reintroduce ABI-009 at the lower dose level (refer to Table 3). Reintroduction of ABI-009 may occur once.
Grade 3 (except hyperlipidemia*) (pneumonitis management detailed separately in 8.7.4)	Interrupt ABI-009 until recovery to grade 1 or better. Then reintroduce ABI-009 at the lower dose level. For pneumonitis consider the use of a short course of corticosteroids. Reintroduction of ABI-009 may occur once.
Grade 4	Discontinue ABI-009.
Hematological toxicity	
Grade 2 Thrombocytopenia (platelets <75, $\geq 50 \times 10^9/L$)	Interrupt ABI-009 until recovery to grade 1 or better ($>75 \times 10^9/L$). Then reintroduce ABI-009 at initial dose. If thrombocytopenia again returns to grade 2, interrupt ABI-009 until recovery to grade 1 or better. Then reintroduce ABI-009 at the lower dose level (refer to Table 3). Reintroduction of ABI-009 may occur once.
Grade 3 Thrombocytopenia (platelets <50, $\geq 25 \times 10^9/L$)	Interrupt ABI-009 until recovery to grade 1 or better (platelets $\geq 75 \times 10^9/L$). Then resume ABI-009 at one dose level lower. If grade 3 thrombocytopenia recurs, discontinue ABI-009.
Grade 4 Thrombocytopenia (platelets <25 $\times 10^9/L$)	Discontinue ABI-009.

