Grade 3 Neutropenia (neutrophils <1, $\geq 0.5 \times 10^9/L$)	Interrupt ABI-009 until recovery to grade 1 or better (neutrophils $\geq 1.5 \times 10^9/L$). Then resume ABI-009 at the initial dose. If ANC again returns to Grade 3, hold ABI-009 until the ANC $\geq 1.5 \times 10^9/L$. Then resume ABI-009 dosing at the lower dose level (refer to Table 3). Discontinue participant from study drug for a third episode of grade 3 neutropenia.
Grade 4 Neutropenia (neutrophils <0.5 $\times 10^9/L$)	Interrupt ABI-009 until recovery to grade 1 or better (neutrophils $\geq 1.5 \times 10^9/L$). Then resume ABI-009 at the lower dose level (refer to Table 3). If grade 3 or grade 4 neutropenia occurs despite this dose reduction, discontinue ABI-009.
Grade 3 febrile neutropenia (not life-threatening)	Interrupt ABI-009 until resolution of fever and neutropenia to grade 1 or better. Hold further ABI-009 until the ANC $\geq 1,500/\text{mm}^3$ and fever has resolved. Then resume ABI-009 at the lower dose level (refer to Table 3). If febrile neutropenia recurs, discontinue ABI-009.
Grade 4 febrile neutropenia (life-threatening)	Discontinue ABI-009.
Any hematological or non-hematological toxicity requiring interruption for ≥ 3 weeks	Discontinue ABI-009.

*Grade 3 hyperlipidemia (hypercholesterolemia and/or hypertriglyceridemia) should be managed using medical therapies.

All interruptions or changes to study drug administration must be recorded.

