11.4 Monitoring suspected toxicities for discontinued participants

Participants whose treatment is permanently discontinued due to an adverse event or abnormal laboratory value suspected to be related to ABI-009 must be followed at least weekly until the adverse event or abnormal laboratory resolves or returns to grade 1. If a participant requires a dose delay of ≥ 3 weeks from the intended day of the next scheduled dose, then the participant must be discontinued from the study.

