12 DISCONTINUATION AND REPLACEMENT OF PARTICIPANTS

12.1 Early Permanent Discontinuation of ABI-009 Dosing

A participant may be permanently discontinued from ABI-009 dosing at any time if the participant, the investigator, or the Sponsor feels that it is not in the participant's best interest to continue. The following is a list of possible reasons for early permanent discontinuation of study treatment:

- Participant or participant's legal representative decision
- Protocol violation
- C-SSRS serious suicidal ideation score is increased to a 4 rating
- Death
- Pregnancy
- Refusal to complete patient diary, QOLCE, NCBRF, or C-SSRS questionnaires

If a participant is permanently discontinued from dosing early due to an adverse event, the participant will be followed and treated by the Investigator until the abnormal parameter or symptom has resolved or stabilized.

All participants who permanently discontinue study dosing early should come in for an early permanent discontinuation of study treatment visit as soon as possible and complete all remaining scheduled visits and procedures.

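### Table 5 (Grades 2 and 3), Section 8.6 and Section 11.4 remove a participant from the study after 3 weeks of unresolved pneumonitis or dose delay, whereas Table 4's last row and Section 12.1 stop only ABI-009 and keep follow-up going

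*Combined protocol and SAP*

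**What the plan says.** Three places end study participation:

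- Section 8.7.4, Table 5, Grades 2 and 3: "Participants will be withdrawn from the study if they fail to recover to" Grade 1 or better within 3 weeks. The sentence stands in the dose-adjustment column of both rows.
- Section 8.6 text, for a dose delay of 3 weeks or more: "then the participant must be discontinued from the study or may resume only with the approval of the Principle Investigator".
- Section 11.4, second sentence, for the same delay: "then the participant must be discontinued from the study". The investigator exception of 8.6 is absent here.

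Two places stop only the drug:

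- Table 4, last row: "Any hematological or non-hematological toxicity requiring interruption for" 3 weeks or more leads to discontinuation of ABI-009.
- Table 5, Grade 4: "Discontinue ABI-009".

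Two places keep follow-up going once dosing has stopped:

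- Section 11.4, first sentence, covers "Participants whose treatment is permanently discontinued due to an adverse event or abnormal laboratory value" suspected to be related to ABI-009. Such participants "must be followed at least weekly until the adverse event or abnormal laboratory resolves or returns to grade 1".
- Section 12.1 requires an event that ended dosing to be followed until it resolves or stabilizes. It also asks everyone who stops dosing early to "complete all remaining scheduled visits and procedures".

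**The concern.** Safety is the primary objective, and Section 8.7.4 describes non-infectious pneumonitis as a class effect that has on rare occasions been fatal. A rule that sends a participant off study while that event is unresolved works against the objective. Section 9.1.14 ends adverse event capture when the participant leaves the study. Section 5.1 makes medically determined withdrawal a primary tolerability endpoint, so the rule itself can generate an endpoint event. Section 12.4 does not replace participants who have been dosed.

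The ordering is also odd: an unresolved Grade 2 event ends study participation, whereas Grade 4 ends only the drug.

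The wording matters most for participants who have received all three doses. The duties in 11.4 and 12.1 are triggered by early discontinuation of treatment, which has not happened to them.

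**Working it through.** The plan gives no figure on this point to reproduce. The check is a comparison of rules followed by date arithmetic.

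**1. The rules side by side**

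| Place | Trigger | Consequence |
|---|---|---|
| Table 5, Grades 2 and 3 | Not Grade 1 or better within 3 weeks | Leaves the study |
| 8.6 text | Dose delay of 3 weeks or more | Leaves the study, unless the investigator approves resuming |
| 11.4, second sentence | Dose delay of 3 weeks or more | Leaves the study |
| Table 4, last row | Any toxicity interrupting dosing for 3 weeks or more | Stops ABI-009 |
| 11.4, first sentence | Treatment stopped for a suspected related event | Event followed weekly |
| 12.1 | Dosing stopped early | Event followed; remaining visits completed |

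A participant whose dosing is interrupted for 3 weeks by pneumonitis meets both sets of rules. One set ends participation; the other keeps the visits.

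**2. Grade 2 managed by dose reduction**

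Table 5 allows a reduced dose for Grade 2 without interruption. Section 8.4.1 spaces doses 5 to 9 days apart, so dose 3 falls 2 × 5 = 10 to 2 × 9 = 18 days after dose 1. For onset at or after dose 1, a 3-week clock from onset ends on day 21 or later, at least 21 − 18 = 3 days after dose 3. If the reduced doses are given within that spacing, the withdrawal sentence never stops a dose.

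Example with weekly dosing: onset at the dose 2 visit (day 7) gives withdrawal on day 7 + 21 = 28. Dose 3 was on day 14, so withdrawal falls 14 days after dose 3, and 90 − 14 = 76 of the 90 follow-up days are lost.

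**3. Onset after dose 3**

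Inputs: follow-up to 90 days after dosing (10.6) and a 30-day DLT window (8.5). Assumptions: the 3 weeks run from onset, and both periods are counted from dose 3.

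- Withdrawal day = onset + 21
- Follow-up days lost = 90 − (onset + 21)
- DLT-window days after withdrawal = max(0, 30 − (onset + 21))

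| Onset, days after dose 3 | Withdrawal day | Follow-up days lost | DLT-window days after withdrawal |
|---|---|---|---|
| 0 | 21 | 69 of 90 (77%) | 9 |
| 7 (Visit 6) | 28 | 62 of 90 (69%) | 2 |
| 14 | 35 | 55 of 90 (61%) | 0 |

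If the clock starts later than onset, the loss shrinks by one day for each day of delay.

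**4. Visits**

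With the ±7-day windows of 10.6, Visit 7 is open on days 23 to 37, Visit 8 on days 53 to 67 and Visit 9 on days 83 to 97. Withdrawal on day 21 to 35 comes before the windows of Visits 8 and 9 open. Under 12.3 a withdrawing participant is encouraged, not required, to attend an exit visit with the procedures of the next scheduled visit. That can bring Visit 7 or Visit 8 procedures forward. Neither includes the C-SSRS, which after dosing is given at Visits 6 and 9 only (10.5, 10.6). One of two post-dosing C-SSRS assessments can therefore be lost, and the C-SSRS is a primary tolerability endpoint (5.1).

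**5. With the wording corrected**

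If Table 5 stopped only ABI-009 and remaining visits were kept, the rule would remove no scheduled follow-up.

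**The case against.** The strongest reply is that the Table 5 sentence was never meant for a participant who has finished dosing. It stands in a dose-adjustment column, after instructions to reduce, interrupt, hold or restart. Where 8.6 and 11.4 define their 3-week limit, it runs from the intended day of the next dose, and after dose 3 there is none. This is a fair account of likely intent, but Table 5 sets no such limit. Step 2 also shows that the reach past dose 3 arises for onset during dosing, whenever Grade 2 is handled by dose reduction on schedule.

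Some stronger readings are tempting, and the documents do not support them:

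- **That follow-up of the pneumonitis stops for everyone.** Where dosing is permanently stopped for a related event, 11.4 and 12.1 still require that event to be followed. The 10.7 visit includes C-SSRS, QOLCE, NCBRF and adverse events. For any grade, Table 5 also repeats imaging until return to baseline.
- **That the DLT window is left open.** For the onsets in step 3 the gap is at most 9 days. Appendix 1 has adverse event review at Visit 7, so an exit visit held on day 30 or later with those procedures would record a worsening before then.
- **That Visits 8 and 9 are always lost.** If Visit 7 has already been held, the exit visit carries Visit 8 procedures.
- **That Table 5 stands alone, or contradicts its own Grade 4 row.** Sections 8.6 and 11.4 agree with Table 5 on study removal. The Grade 4 row concerns a different grade, so it is an odd ordering, not a contradiction. Table 4's Grade 2 and 3 rows defer pneumonitis to 8.7.4; only its last row, which has no such exception, conflicts.

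The effect on tolerability is also narrow. Section 15.4 tabulates permanent drug discontinuation, so a fully dosed participant would count under the withdrawal endpoint of 5.1 but not in that table.

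**Conclusion.** The rule is wrong as written: low frequency, minor to moderate severity.

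For a participant whose dosing is stopped for related pneumonitis, the fault is contradictory instructions, with possible loss of scheduled visits and of capture of other adverse events. For a participant with Grade 2 managed by dose reduction, or with onset after dose 3, the sentence read literally has no dosing function. It ends adverse event capture with a lung toxicity unresolved, records a fully dosed participant as a medically determined withdrawal, and can lose later follow-up, including the Visit 9 C-SSRS.

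The 69 to 55 lost days rest on the literal reading and on a clock that starts at onset, which Table 5 does not state. Which visits are lost, and whether any of the DLT window goes uncovered, depend on when Visit 7 and the exit visit are held. The documents give no pneumonitis rate for this population, and there may be no case. A single case would be 1 of 3 in an initial cohort, or 1 of 18 at maximum enrollment, on the withdrawal endpoint.

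**What to change.** 1. In Table 5, Grades 2 and 3, replace the withdrawal sentence with: *If not recovered to Grade 1 or better within 3 weeks, permanently discontinue any remaining ABI-009; the participant stays on study, completes all remaining visits (12.1), and the event is followed until resolved or stabilized.*
2. In 8.6 and in the second sentence of 11.4, make the discontinuation one from ABI-009 instead of from the study. Whether to keep the investigator-approval exception in 8.6 is for the sponsor to decide.

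The weekly follow-up in 11.4 stays as it is for those whose treatment is discontinued. No new weekly duty is needed for onset after dose 3.

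The cost is amendment wording in three sections. Affected participants attend visits already in the schedule and may still leave voluntarily under 12.3. Sample size and imaging do not change.

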8.7.5 Management of Febrile neutropenia

Febrile neutropenia should be managed according to the local institutional guidelines. Measures include laboratory testing, blood and urine cultures, and institution of broad spectrum antibiotics.

8.7.6 Management of Diarrhea

Following the loperamide dosing guidelines in Table 8 for participants experiencing diarrhea is recommended. Prophylactic administration is NOT recommended. Participants are advised to call with first signs of poorly formed stools or an increased frequency of bowel movements.

Table 6. Weight Specific Guidelines for Therapeutic Use of Loperamide

Weight (kg)	Initial (Loading) Loperamide dose (mg)	Subsequent daytime loperamide dose	Subsequent nighttime loperamide dose
8-10	1	0.5 mg q 3h	0.75 mg q4h
10-20	1	1 mg q 3h	1mg q 4h
20-30	2	1mg q 3h	2mg q 4h
30-43	2	1mg q 2h	2 mg q 4h
>42	4	2mg q 2h	4 mg q4h

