2.1 Risk / Benefit Assessment

The mTOR inhibitors (rapamycin/sirolimus, temsirolimus and everolimus) as a class have similar side effects and safety profiles and one can refer to the package inserts of the marketed mTOR inhibitors for safety information. No new side effects were noted with ABI-009 (see investigator brochure).

The safety data available in the literature to date for all completed controlled and uncontrolled clinical studies suggest that: (a) mTOR inhibitors are generally well tolerated at both daily and weekly dose schedules, and (b) mTOR inhibitors give a favorable safety profile, with adverse events (AEs) being manageable, reversible, and non-cumulative. Most common adverse reactions (incidence $\geq 10\%$) associated with mTOR inhibitors are stomatitis, rash, fatigue, asthenia, diarrhea, anorexia, nausea, mucosal inflammation, vomiting, pneumonitis, cough, peripheral edema, infections, dry skin, epistaxis, pruritus, and dyspnea. The most common grade 3-4 adverse reactions (incidence $\geq 2\%$) were infections, stomatitis, fatigue, and pneumonitis. Non-infectious pneumonitis is a class effect of rapamycin derivatives, and some of these cases have been severe and on rare occasions, fatal outcomes have been observed.

mTOR inhibitors have immunosuppressive properties and may predispose patients to bacterial, fungal, viral or protozoan infections, including infections with opportunistic pathogens. Localized and systemic infections, including pneumonia, other bacterial infections, invasive fungal infections, such as aspergillosis or candidiasis and viral infections including reactivation of hepatitis B virus, have been described in patients taking mTOR inhibitors. Some of these infections have been severe (e.g. leading to respiratory or hepatic failure) and occasionally have had a fatal outcome.

The most common laboratory abnormalities (incidence $\geq 50\%$) associated with mTOR inhibitors are anemia, hypercholesterolemia, hypertriglyceridemia, hyperglycemia, lymphopenia, and increased creatinine. The most common grade 3-4 laboratory abnormalities (incidence $\geq 3\%$) were lymphopenia, hyperglycemia, anemia, hypophosphatemia, and hypercholesterolemia.

Comprehensive clinical safety data and nonclinical toxicology information are available for long term dosing with rapamycin and other mTOR inhibitors, which have been included in previous regulatory submissions with ABI-009 (IND 125669 and Investigator's Brochure, version 5.0).

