6.2 Inclusion Criteria

1. Written informed consent (and assent when applicable) obtained from participant or participant's legal representative
2. Be willing and able to adhere to the study visit schedule and other protocol requirements
3. Male or female ≥ 3 and ≤ 26 years of age at Visit 1
 - b. Because no dosing or adverse event data are currently available on the use of ABI-009 or other mTOR inhibitors in participants <3 years of age, these young children are excluded from this study.
4. Documentation of a diagnosis of medically intractable epilepsy as defined by the failure of at least 2 appropriately dosed and tolerated AEDs to eliminate all clinical seizures over a 6-month period, prior to epilepsy surgery
5. Documentation of resective epilepsy surgery following appropriate pre-surgical evaluation
6. Documentation of continued clinical seizures that persist at least 3 months following resective epilepsy surgery. In order to proceed with enrollment and study drug initiation, participants will have to have had >8 seizures in the last 30 days without 2 consecutive weeks of seizure freedom, as noted by a daily seizure diary.
7. Documentation that the participant is not a candidate for *or* refuses any additional resective epilepsy surgery
8. Participants must have adequate bone marrow function (ANC $\geq 1,000/\text{mm}^3$, platelet count of $\geq 100,000/\text{mm}^3$, and hemoglobin $\geq 9 \text{ gm/dL}$) before study drug dosing.
9. Participants must have adequate liver function (SGPT/ALT ≤ 5 times ULN and bilirubin ≤ 5 times ULN) before study drug dosing.
10. Participants must have adequate renal function, defined as: Creatinine clearance or radioisotope GFR $\geq 70\text{mL/min}/1.73 \text{ m}^2$ **or** a serum creatinine before study drug dosing based on age/gender as follows:

Age	Maximum Serum Creatinine (mg/dL)	
	Male	Female
3 to < 6 years	0.8	0.8
6 to < 10 years	1	1
10 to < 13 years	1.2	1.2
13 to < 16 years	1.5	1.4
≥ 16 years	1.7	1.4

The threshold creatinine values in this table were derived from the Schwartz formula for estimating GFR utilizing child length and stature data published by the CDC.

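### Minor: the loperamide table gives two doses, one twice the other, for weights above 42 and up to 43 kg, with no rule to choose between them

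*Combined protocol and SAP*

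**What the plan says.** Section 8.7.6 (Management of Diarrhea) introduces the dosing table with "Following the loperamide dosing guidelines in Table 8 for participants experiencing diarrhea is recommended". The table directly below that sentence is headed "Table 6. Weight Specific Guidelines for Therapeutic Use of Loperamide". Its last two rows, in the order weight (kg), loading dose (mg), daytime dose and nighttime dose, read:

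- "30-43 2 1mg q 2h 2 mg q 4h"
- ">42 4 2mg q 2h 4 mg q4h"

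The rest of the section advises against prophylactic use and asks participants to call at the first signs. It gives no rule for a weight that fits two rows, no maximum daily dose, and no definition of daytime and nighttime hours.

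Two other places bear on whether the case can arise. Section 6.2 admits "Male or female ≥ 3 and ≤ 26 years of age at Visit 1", and the eligibility criteria set no weight limit. Section 2.1 lists diarrhea among the class reactions seen in 10% or more: "associated with mTOR inhibitors are stomatitis, rash, fatigue, asthenia, diarrhea".

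**The concern.** A weight-based dosing table should return one dose for each weight. This one returns two for any weight above 42 and up to 43 kg, and they differ by a factor of two in every column. Two clinicians who each followed the table correctly could advise the same participant differently, and neither would have departed from the protocol.

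The trial enrols children, adolescents and young adults, so a weight of 42 to 43 kg is eligible. What is at stake is consistent supportive care for an occasional participant. The primary and secondary endpoints, the escalation rules and the planned analyses do not depend on it.

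**Working it through.** **Inputs.** The row limits and doses come from Table 6 in section 8.7.6. The plan states no daily totals, so there is no plan figure to reproduce.

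**Step 1: which rows a weight falls in, limits taken as printed.**

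| Weight (kg) | Rows that apply |
|---|---|
| 42.0 | 30-43 only |
| 42.1 | 30-43 and >42 |
| 42.5 | 30-43 and >42 |
| 43.0 | 30-43 and >42 |
| 43.1 | >42 only |

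The overlap is the interval above 42 and up to 43 kg.

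**Step 2: dose ratio, >42 row over 30-43 row.** Loading 4/2 = 2.0; daytime 2/1 = 2.0 (both every 2 h); nighttime 4/2 = 2.0 (both every 4 h).

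**Step 3: maintenance per 24 h, loading dose excluded.**

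- 30-43 row: day 1 mg / 2 h = 0.5 mg/h; night 2 mg / 4 h = 0.5 mg/h; 24 × 0.5 = 12 mg.
- >42 row: day 2 mg / 2 h = 1.0 mg/h; night 4 mg / 4 h = 1.0 mg/h; 24 × 1.0 = 24 mg.

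Within each row the day and night rates are equal, so 12 against 24 mg holds for any day/night split. With the loading dose added, the totals are 2 + 12 = 14 mg and 4 + 24 = 28 mg.

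**Step 4: per kilogram, in context.**

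- Lower reading: 12/42 = 0.286 and 12/43 = 0.279 mg/kg per 24 h.
- Upper reading: 24/42 = 0.571 and 24/43 = 0.558 mg/kg per 24 h.
- Undisputed neighbours: 12/42 = 0.286 at exactly 42 kg, and 24/43.1 = 0.557 just above the overlap.
- 10-20 kg row, assuming 12 h day and 12 h night: 4 × 1 + 3 × 1 = 7 mg, which is 7/10 = 0.70 mg/kg at 10 kg and 7/12 = 0.58 mg/kg at 12 kg.

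The upper reading is therefore no higher per kilogram than doses the table already gives elsewhere.

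**Step 5: shared endpoints in the lower rows (same 12 h / 12 h assumption).**

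| Weight (kg) | Rows | Loading (mg) | Maintenance per 24 h (mg) |
|---|---|---|---|
| 10 | 8-10 / 10-20 | 1 / 1 | 4 × 0.5 + 3 × 0.75 = 4.25 / 7 |
| 20 | 10-20 / 20-30 | 1 / 2 | 7 / 4 × 1 + 3 × 2 = 10 |
| 30 | 20-30 / 30-43 | 2 / 2 | 10 / 12 |

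These are single points. Only the last pair of rows overlaps over an interval.

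**Step 6: how many participants.** The maximum enrolment is 18. The share of participants in the 1 kg band is not in the documents; I assume 1 to 3%. For diarrhea I take 10% (the class threshold in section 2.1) to 23% (6 of 26 in the completed adult study in section 1.11, at 45-150 mg/m²). Neither rate was observed at this trial's 1-20 mg/m².

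- Low: 18 × 0.01 × 0.10 = 0.018
- High: 18 × 0.03 × 0.23 = 0.124

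**Step 7: cross-reference.** The text sends the reader to Table 8. The protocol's numbered tables run from 1 to 7, and the loperamide table is Table 6.

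**The case against.** The strongest reply is that almost nothing follows from this. On the figures above, the expected number of affected participants is between 0.02 and 0.12 over the whole trial. The table is a recommendation, a clinician must pick one dose in any case, and the 12 against 24 mg contrast assumes a full day of uninterrupted dosing, so it is a ceiling. All of this stands, and it is why the point is rated minor.

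Two further objections are partly right.

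- The defect turns on one digit, 42 or 43, in a table taken from a PDF, so a misreading cannot be excluded altogether. Nothing suggests one: the table is intact and its other rows read cleanly. Checking the source table would settle it.
- The 0.70 mg/kg comparison at 10 kg uses a weight that is itself in two rows; on the 8-10 kg row it would be 4.25/10 = 0.425 mg/kg. The comparison does not depend on that weight, because at 12 kg only the 10-20 kg row applies and gives 0.58 mg/kg, still above 0.571.

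It can also be said that no calculation in the protocol is wrong and that this is a row-boundary slip. That is a fair description, but the slip sits in an operative dosing instruction that contradicts itself, and nothing elsewhere in the protocol resolves it.

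**Conclusion.** The concern holds as a minor point. As printed, Table 6 assigns weights above 42 and up to 43 kg to two rows whose doses differ two-fold in every column (12 against 24 mg per 24 h of maintenance), and section 8.7.6 offers no tie-break. The overlap, the ratio and the daily totals for these two rows need no assumption beyond the printed table and dosing through a full 24 h. The totals for the lower rows assume a 12 h / 12 h split, and the expected count rests on the assumed 1-3% and 10-23%.

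This is not a claim of overdose. The reference to Table 8 is a clerical slip and adds no weight.

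**What to change.** In the next amendment:

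1. Check the table against its source and set a single cut-off, either 30-42 with >42 or 30-43 with >43. The clinical team must decide which dose is right for 42 to 43 kg.
2. Assign exactly 10, 20 and 30 kg to one row each, for example by writing each band as from its lower limit to below its upper limit. The 10 kg case is unlikely at age 3 or over but belongs in the same edit.
3. Change Table 8 to Table 6 in the sentence above the table.

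The cost is one table correction and one cross-reference. Endpoints, analysis and enrolment are unaffected.
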